The purpose of this study is to prospectively compare preoperative (neoadjuvant) SRS/SRT to postoperative (adjuvant) SRS/SRT in patients undergoing surgical resection for brain metastases.

Hypothesis, Objectives, and Outcomes

We hypothesize that neoadjuvant SRS/SRT prior to surgical resection of brain metastases will result in improved freedom from Central Nervous System (CNS) events when compared to adjuvant SRS/SRT after surgical resection.

Primary Objectives

- Our primary objectives are: (1) to determine the *Time to a Central Nervous System* (*CNS*) *Composite Event* (*CE*) in subjects who receive either neoadjuvant (preoperative) SRS/SRT or adjuvant (post-operative) SRS/SRT for their brain metastases, and (2) to compare the two treatment arms for evidence of improved Time to a CNS CE among subjects who received neoadjuvant SRS/SRT.
 - A CNS CE will consist of one of the following three events: Local Recurrence (LR) of the treated lesions, symptomatic radiation necrosis (SRN) to the treated lesions, or development of leptomeningeal disease (LMD). See below for detailed definitions of LR, SRN, and LMD.
 - Time to a CNS CE, the primary outcome, will be measured as the time from the date of randomization to the date of a documented LR, SRN, or LMD, whichever occurs first.
 - Death before occurrence of a CNS CE will be treated as a competing risk. Study participants who are alive and have yet to experience a CNS CE at their last evaluation will be right-censored for Time to CNS CE on the date of their last evaluation.

Secondary Objectives related to the Primary Objective. Some of our secondary objectives include (a) determining in each study subject the *secondary outcomes* listed below, and (b) comparing the treatment arms for evidence of improvements in these secondary outcomes.

- Index lesion local recurrence (ILLR), a component of CNS CE, will be defined as the development of new nodular contrast enhancement in the surgical bed compared with the immediate postoperative MRI.
- Non-index lesion LR, also a component of CNS CE, will be defined as an increase of more than 25% in the size of any treated non-resected brain lesion.

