Other Secondary Objectives include determining the other secondary outcomes described below, and comparing treatment arms for improvements with neoadjuvant SRS/SRT in (a) the rates of secondary yes/no outcomes such as Local Control, or (b) the 6-month, 12-month, 18-month, month rates of secondary time-to-event outcomes such as Duration of Local Control:

- Local Control.
 - Local Control will be defined as Complete Response [CR], Partial Response [PR], or Stable Disease [SD] of the index lesion resulting from the assigned treatment. It will be determined at the first evaluation following successful completion of either neoadjuvant or adjuvant SRS/SRT of all metastatic lesions and surgical resection of the index lesion.
 - Stratified by GTR or STR, piecemeal vs en bloc resection

- Treatment Failure will be defined either as Progressive Disease [PD] during the assigned treatment, or as the absence of Local Control at the first evaluation following successful completion of the assigned treatment.
- Duration of Local Control (DLC) will be measured as the time from the date when Local Control is first documented to the date when:
 - the treated lesions show documented evidence of LR or PD, or
 - the patient undergoes whole-brain radiotherapy, repeat SRS, repeat surgical intervention
- Time to distant in-brain failure.
 - Distant in-brain failure (DiBF) will be defined as the occurrence of any new parenchymal lesion outside of the planning target volume.
 - Time to DiBF will be measured as the time from the date of randomization to the date of occurrence of the DiBF. Death before occurrence of DiBF will be treated as a competing risk. Study subjects who are alive and free of DiBF at their last evaluation will be right-censored for Time to DiBF on the date of their last evaluation.
- Overall survival.
 - Overall survival (OS) will be measured as the time from the randomization date to the date of death for any reason. Study participants who are still alive at last follow-up will be right-censored for OS on the date of their last follow-up.
- Time to systemic therapy.
 - Time to initiation or re-initiation of systemic therapy will be measured as the time from the date when the assigned treatment (neoadjuvant versus adjuvant SRS/SRT) is successfully completed to the date when the systemic therapy is initiated or re-initiated.

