- Time to subsequent brain treatment, including whole-brain radiotherapy (WBRT), will be measured as the time from the date when the assigned treatment is successfully completed to the date when the WBRT or other subsequent treatment is initiated.
- Radiation/Surgery toxicity
 - o The rate of symptomatic (≥grade 2) radiation/surgery toxicity

 Incidence of adverse events as graded by the National Cancer Institute (NCI) Common Terminology Criteria for Adverse Events (CTCAE) version 5.0

Study Design and Procedures

Design: This pilot study is a randomized, open-label, 2-arm active-controlled phase II clinical trial conducted at a single study site (UAMS) located in central Arkansas. Prospective enrollees will be screened based on the inclusion/exclusion criteria listed below in the *Study Population* section. Study-eligible candidates who agree to participate will be assigned by randomization to one of the 2 treatment arms shown in the table below:

Treatment Arm	Intervention/treatment
Experimental: Arm I (pre-operative SRS/SRT)	Radiation: Stereotactic Radiosurgery Undergo SRS/SRT Other Names:
Patients undergo SRS or SRT within 15 days of randomization followed by surgery within 15 days of radiation completion. Patients may undergo	Stereotactic External Beam Irradiation
	 stereotactic external-beam radiation therapy
additional SRS or SRT if disease returns after treatment.	stereotactic radiation therapy
	Stereotactic Radiotherapy
	 stereotaxic radiation therapy
	 stereotaxic radiosurgery
Active Comparator: Arm II (post- operative SRS/SRT) Patients undergo surgery within 15 days of randomization followed by standard-of-care SRS or SRT within 30	Undergo SRS/SRT Other Names: • Stereotactic External Beam Irradiation
	 stereotactic external-beam radiation therapy
days of surgery. Patients may undergo additional SRS or SRT if disease	stereotactic radiation therapy
returns after treatment.	Stereotactic Radiotherapy
	 stereotaxic radiation therapy
	stereotaxic radiosurgery

The dose, volume and fractionation of radiotherapy will be at the discretion of the radiation oncologist at the time of SRS/SRT depending on the size, location, and proximity to critical structures. Before treatment commences, each study participant will be stratified according to two stratification factors:

- Size of Index Lesion (<3 cm versus ≥3 cm)
- Number of Brain Metastases (4 or fewer versus 5 or more)

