- Largest lesion > 5cm
- Pregnancy
- Known allergy to gadolinium, pacemaker, or other contraindication such as metal implant that is not safe for MRI. Patients with MRI-compatible implants are eligible.
- Patients who have local recurrence of previously treated brain metastasis.
- Patients who have received prior WBRT.
- Inherited radiation hypersensitivity syndromes
 - Ataxia Telangiectasia, Nijmegen Breakage Syndrome, Fanconi Anemia, DNA Ligase IV, Mre 11 deficiency, SCID, Bloom's syndrome
- Collagen vascular diseases
 - Active systemic lupus erythematous (SLE), scleroderma, mixed connective tissue disorder, polymyositis or dermatomyositis, CREST Syndrome
- Cytotoxic Chemotherapy within 7 days prior to SRS/SRT.
 - Molecularly targeted therapies, including immune-modulatory drugs, can be given within 7 days of SRS/SRT at the discretion of the treating physician.
- Patients who received anti-VEGF therapy within 6 weeks prior to enrollment, as there is increased risk of fatal brain hemorrhage with surgical resection.
- Treatment plan respecting normal tissue tolerances using dose fractionation specified within the protocol cannot be achieved.

Risks and Benefits

Potential risks

A risk to study participants is the potential for loss of confidentiality of study data. Measures to protect the confidentiality of study data will be implemented as described in the Data Handling and Recordkeeping section below.

A risk to study participants is that pathologic confirmation of target lesion is not available. There is a possibility that a lesion (that is radiologically/clinically consistent with a brain metastasis) may represent an infectious/inflammatory process or a separate malignancy. In that case, neoadjuvant SRS/SRT may not represent the optimal treatment option. This risk is being minimized by only including patients with biopsy proven malignancies (where the biopsy was performed at the primary cancer site or another metastatic site) but there is still a small risk that the target lesion may represent an infectious/inflammatory process or a separate malignancy. However, this risk is not greater than the standard of care for brain metastases diagnosed by radiographic imaging or clinical findings, as these patients may receive surgery and/or radiation of the target lesion without pathologic confirmation.

A risk to study participants is the increased risk of delayed wound healing with neoadjuvant SRS/SRT compared to adjuvant SRS/SRT.

Potential benefits

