Data Safety Monitoring Plan: The study will be monitored by the investigators to ensure that the rights and well-being of human subjects are protected, that the data are accurate, complete and verifiable from source documents and that the trial is conducted in compliance with currently approved protocol/amendments. The PI and sub-Investigators will review study conduct on an ongoing basis. The PI will assure that all protocol deviations, AEs, and SAEs are reported to the IRB according to the applicable regulatory requirements.

Specimen Handling and Storage

Tumor specimens will be collected from surgical resection and stored by the Department of Pathology and kept as part of standard of care. No samples will be collected specifically for use in this study at this time.

Data Analysis

Statistical analysis plan

Patient characteristics will include patient demographics, disease characteristics of the primary tumor, and relevant characteristics (number, location, size, etc.) of the brain metastases being treated. Patient characteristics will be summarized by treatment arm with medians, quartiles, and ranges for numeric characteristics, or with numbers and percentages for category characteristics. Each characteristic then will be assessed for imbalance between treatment arms with Wilcoxon's rank-sum test for numeric characteristics. The imbalance assessments will consist of 2-sided tests that employ the standard α =0.05 significance level.

Time to a CNS CE, the primary outcome, will be visualized with Cumulative Incidence (CI) curves computed using Kaplan-Meier methodology, summarized by treatment group as CI proportions at 6, 12, and 18 months, and compared for difference using the Fine and Gray model for equality of CI functions when death before a CNS CE is treated as a competing risk. Times to each of the individual CNS events (LR, SRN, LMD, DiBF, and WBRT) will be analyzed the same way, except that each Fine and Gray model will have the competing risk be death before the individual event being analyzed. Overall survival will be visualized using standard Kaplan-Meier curves and compared for differences via the log-rank test. Because this is a pilot study, all time-to-event outcomes will be compared for evidence of improvement on the pre-operative SRS/SRT arm using 1-sided tests that employ an α =0.10 significance level.

Sample size, power, and study duration

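### Time to systemic therapy and time to subsequent brain treatment start at completion of the assigned treatment, not at randomization, so the arms lack a common origin and non-completers have none

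*Combined protocol and SAP*

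**What the plan says.** Under Other Secondary Objectives, time to systemic therapy is "measured as the time from the date when the assigned treatment (neoadjuvant versus adjuvant SRS/SRT) is successfully completed", up to the start or restart of systemic therapy. Time to subsequent brain treatment "will be measured as the time from the date when the assigned treatment is successfully completed to the date when the WBRT" or another subsequent treatment starts.

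The primary outcome, LR, LMD, SRN, DiBF and overall survival all run from randomization. For example, "Time to DiBF will be measured as the time from the date of randomization to the date of occurrence of the DiBF".

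The treatment-arm table in Study Design and Procedures sets the windows. Arm I: "Patients undergo SRS or SRT within 15 days of randomization followed by surgery within 15 days of radiation completion". Arm II: "Patients undergo surgery within 15 days of randomization followed by standard-of-care SRS or SRT within 30" days of the operation.

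The opening of Other Secondary Objectives says the arms will be compared for improvement with neoadjuvant treatment. The Statistical analysis plan adds "Times to each of the individual CNS events (LR, SRN, LMD, DiBF, and WBRT) will be analyzed the same way" as the primary outcome, that is, by Fine and Gray with death as the competing risk. It tests every time-to-event outcome 1-sided at 0.10. Neither definition gives a censoring rule, a rule for patients who never complete, or a rule for therapy begun before completion. No analysis population is stated.

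**The concern.** A randomized comparison needs a time origin that every randomized patient has and that the assigned arm does not influence. Completion of treatment fails on both counts. It follows randomization, its permitted date differs by arm because the two sequences have different windows, and some patients never reach it. The comparison is then among completers, on clocks that start at different distances from randomization.

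For systemic therapy, finishing local treatment sooner is one way in which the pre-operative sequence could help, and this origin removes exactly that part of the difference. For subsequent brain treatment, a patient who receives something else in place of the assigned SRS/SRT has no start date, so the event cannot be counted.

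**Working it through.** The plan gives no figure on this point; its one power calculation concerns the primary outcome. The inputs are the windows in the treatment-arm table, 52 patients per arm, and the planning rate of 32% per year for death before a CNS event (Sample size, power, and study duration).

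**1. What completion means.** The Local Control definition refers to completing SRS/SRT of all metastatic lesions and resection of the index lesion. The Treatment Failure definition next to it shortens this to completing the assigned treatment, the term both disputed outcomes use. Completion is therefore the later of the two procedures.

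**2. Permitted completion date** (days from randomization, ignoring the few days that a fractionated course may add):

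| | Arm I | Arm II | Gap |
|---|---|---|---|
| Last allowed day | 15 + 15 = 30 | 15 + 30 = 45 | 15 |
| Mid-window | 7.5 + 7.5 = 15 | 7.5 + 15 = 22.5 | 7.5 |

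**3. Systemic therapy, equal lag L after the last procedure, at the window limits.** From randomization: 30 + L v 45 + L, so Arm I starts 15 days sooner. From completion: L v L, no difference. With L = 14, the dates are day 44 v day 59, yet both arms record 14 days. At mid-window the hidden gain is 7.5 days.

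**4. Same start date in both arms, at the window limits.** Treatment on day 90 is recorded as 90 − 30 = 60 days in Arm I and 90 − 45 = 45 days in Arm II. For subsequent brain treatment, where later is better, this leans toward Arm I.

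**5. How much the origin alone matters for brain treatment.** The documents give no WBRT rate, so this is a simulation under assumptions: 52 per arm, uniform 3-year accrual, follow-up to 4.5 years, death hazard 0.32 per year, a Fine and Gray type test, completion at the window limits, WBRT arising only after completion at 0.10 or 0.20 per year, and no WBRT in place of SRS/SRT.

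| Assumed WBRT hazard | Type I error: randomization v completion | Power if halved in Arm I: randomization v completion |
|---|---|---|
| 0.10 | 9.4% v 10.3% | 44.3% v 46.2% |
| 0.20 | 8.7% v 9.9% | 58.1% v 60.8% |

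The effect is 1 to 3 points, slightly toward Arm I.

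**6. Patients without an origin.** Deaths before the last allowed completion day, 52 × (1 − exp(−h × days/365.25)):

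- h = 0.32: 1.35 in Arm I (day 30) and 2.01 in Arm II (day 45).
- h = −ln(1 − 0.32) = 0.386: 1.62 and 2.41.

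The exclusion of patients with under 3 months' expected survival may make early deaths fewer. Non-completion for any reason is not given; an assumed 2% to 15% of 104 would be about 2 to 16 patients.

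**The case against.** Time from completion answers a fair clinical question: how long after local treatment does the next therapy begin? The windows are upper limits, so the actual gap may be below 15 days. These are two of many secondary outcomes in a pilot phase II trial. All of this stands and limits the severity. It does not justify the origin for a between-arm test, and it does not supply a start date for non-completers.

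Four stronger readings are tempting, and the documents do not support them.

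- **Completion means SRS/SRT alone (day 15 v day 45).** The bracket in the systemic-therapy definition might suggest this, but it reads more naturally as naming the arms, and the Local Control definition includes resection. The 30-day gap falls away.
- **The rule hides a true reduction in WBRT.** A reader might infer that early imaging leads to WBRT, which counts in Arm I but is lost in Arm II when it replaces SRS/SRT. The plan mentions that scan only as a baseline for index-lesion recurrence ("compared with the immediate postoperative MRI"). It does not say that the scan triggers WBRT or how often WBRT replaces SRS/SRT. Adding an assumed 2%, 5% or 10% of patients needing early WBRT to the step 5 model (hazard 0.10, early share and later hazard both halved in Arm I), power is 46.7% v 39.1%, 50.6% v 30.0% and 57.7% v 18.3% (randomization v completion). That loss comes from the assumed share. The model also covers WBRT alone, whereas the defined outcome includes other subsequent brain treatment.
- **A large loss of power for systemic therapy.** With a log-rank test, a gamma lag (mean 30 days, SD 15 to 60), all 104 patients starting and no deaths, detection of the 15-day gain falls from 78–99.7% to about 10%. The plan names no such test for this outcome and gives no lag. Other Secondary Objectives refers to rates at 6, 12 and 18 months. Under the same lags, the 6-month rates from randomization differ by at most about 0.9 points.
- **Routine negative times.** The Exclusion Criteria state "Molecularly targeted therapies, including immune-modulatory drugs, can be given within 7 days of SRS/SRT at the discretion of the treating physician". Continuing a drug is not starting or restarting one, and a dose before SRS/SRT may even precede randomization. What remains is a missing rule for therapy begun between randomization and completion.

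**Conclusion.** The point holds as a defect in two definitions. Both outcomes are compared between randomized arms from a post-randomization date that may be up to 15 days later in Arm II and that some randomized patients do not have. No other section repairs this.

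For systemic therapy, the written rule can cancel a real gain of up to 15 days at the window limits, or 7.5 days at mid-window, if the lag after the last procedure is equal. Calling this a gain assumes that earlier systemic therapy is better, which the plan does not say. For subsequent brain treatment, the origin alone has little effect and slightly favours Arm I; WBRT given in place of SRS/SRT in Arm II would push the other way. Without a rate for that, the net direction and size are not established.

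The primary outcome, its sample size and its power are unaffected. Severity is minor to moderate, and the change is a cheap improvement.

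**What to change.** Reword both definitions as follows.

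- Measure from randomization, in every randomized patient, by assigned arm, with death first as the competing risk. State the censoring date, for example the last evaluation, as for DiBF.
- Count WBRT, or any brain treatment other than the assigned SRS/SRT and resection, on the date it starts, including when it replaces the assigned SRS/SRT.
- Count systemic therapy initiated or re-initiated after randomization on its own start date.
- Report time from completion among completers as a description only, without a between-arm test.

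The cost is the rewording of two definitions. The randomization date and treatment start dates are already needed, and the sample size does not change. The downside is that time from randomization includes the planned treatment period and no longer isolates the delay after local treatment; the descriptive summary keeps that information.

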These stratification factors will be used during the randomization procedure to assure that the treatment arms will be well-balanced with respect to index-lesion size and brainmetastasis number.

On-study Plan: After first signing the IRB-approved Informed Consent form, and after then being stratified according to size of index lesion and number of brain metastases, study participants will be registered and assigned a study number by a clinical research associate (CRA) or Study Coordinator.

Randomization and Treatment Allocation: After the study participant's eligibility has been confirmed, and after the participant has been stratified (see above) and registered in the Research Participant Registration System (RPRS), the study coordinator will do two things. First, the study coordinator will use the RPRS to assign the participant to one of the four possible strata defined by the stratification factors. Then the study coordinator will use the RPRS to randomize the participant in a 1:1 allocation ratio to either Arm I (pre-operative SRS/SRT) or Arm II (post-operative SRS/SRT). The randomizations will be balanced 1:1 on treatment arms within each stratum by using a permuted-blocks approach. Study participants will receive either pre-operative or post-operative SRS/SRT depending on the study arm to which they are randomized. Accordingly the two study arms will follow the treatment schedules shown in the table.

Sample Collection: The extent (gross total or subtotal resection) and technique for surgery (en bloc or piecemeal) will be determined by the neurosurgeon. The pathological specimen will be analyzed and stored by the Department Pathology per standard operating procedure for resected brain tumor specimens.

Follow-up: After completion of radiotherapy and surgery, study subjects will be followed by Brain MRI every 2-3 months for the first year and then every 4-6 months indefinitely (in accordance with National Comprehensive Cancer Network [NCCN] guidelines). Imaging and follow-up can be done sooner than these specified times if clinically indicated. MRI's will be included in study results up to 18 months.

Study Population

Ages Eligible for Study: Sexes Eligible for Study: Accepts Healthy Volunteers: Estimated Enrollment 18 Years and older (Adult, Older Adult)AllNo104 (we anticipate consenting 120 in order to reach this goal)

Inclusion Criteria

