A potential benefit to study participants is the potential improved target delineation with neoadjuvant SRS/SRT. Since the tumor bed can change over time, adjuvant SRS/SRT involves challenges in delineating the target volume of a dynamically changing target, which may lead to geographic miss and increased radiation dose to normal tissues. Improved target delineation with neoadjuvant SRS/SRT may potentially improve local control and reduce toxicity.

A potential benefit to study participants is a potential reduction in the rates of radiation necrosis. With neoadjuvant SRS/SRT, the tumor and adjacent normal tissue that has been irradiated is removed at the time of surgery, reducing the availability of injured tissue and inflammatory reaction needed to precipitate radiation necrosis. In contrast, for adjuvant SRS/SRT, the irradiated tissue remains. Retrospective data suggests the rate of symptomatic radiation necrosis is lower with neoadjuvant SRS/SRT compared to adjuvant SRS/SRT.⁶

A potential benefit to study participants is a potential reduction in the rates of leptomeningeal disease. With neoadjuvant SRS/SRT, the tumor site is "sterilized" and the risk of leptomeningeal disease may be minimized even with tumor spill, as tumor cells may be replicatively dead. Retrospective data suggests the rate of symptomatic radiation necrosis is lower with neoadjuvant SRS/SRT compared to adjuvant SRS/SRT.⁶

A potential benefit to study participants is potential immune system activation against tumor cells. Radiotherapy to an intact tumor may allow for increased immune activation and in situ vaccination, allowing for greater immune response against the tumor cells. Animal models have suggested this benefit but it is not well-studied in human subjects.⁸

Finally, knowledge gained from the study could potentially benefit patients in the future.

Data Handling and Recordkeeping

The Principal Investigators will carefully monitor study procedures to protect the safety of research subjects, the quality of the data and the integrity of the study.

Information will be coded with the key to the code kept separately. Data will be stored securely on UAMS-maintained computers and servers. Only investigators listed on this protocol will have direct access to patient-identifying data. Research assistants, coordinators, and statisticians will only have access to coded data. At the conclusion of the study, the coded data will be de-identified.

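### Toxicity is compared as one pooled radiation/surgery rate, and only for improvement, although the protocol anticipates more delayed wound healing and less radiation necrosis in the pre-operative arm

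*Combined protocol and SAP*

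**What the plan says.** All references are to the combined protocol and SAP.

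- **Other Secondary Objectives, Radiation/Surgery toxicity.** The first item is "The rate of symptomatic (≥grade 2) radiation/surgery toxicity". The second is "Incidence of adverse events as graded by the National Cancer Institute (NCI) Common Terminology Criteria for Adverse Events (CTCAE) version 5.0". Neither has a time window, and neither separates surgical from radiation events.
- **Other Secondary Objectives, opening sentence.** The listed outcomes are to be determined, and the aim of the comparison is "comparing treatment arms for improvements with neoadjuvant SRS/SRT in (a) the rates of secondary yes/no outcomes such as Local Control". The rate of grade 2 or higher toxicity falls in this list and is naturally read as a yes/no outcome.
- **Risks and Benefits, Potential risks.** "A risk to study participants is the increased risk of delayed wound healing with neoadjuvant SRS/SRT compared to adjuvant SRS/SRT".
- **Risks and Benefits, Potential benefits.** "A potential benefit to study participants is a potential reduction in the rates of radiation necrosis", supported by the statement "Retrospective data suggests the rate of symptomatic radiation necrosis is lower with neoadjuvant SRS/SRT compared to adjuvant SRS/SRT".
- **Secondary Objectives related to the Primary Objective.** Symptomatic radiation necrosis (SRN) has its own definition and its own time-to-event outcome. It is also a component of the primary composite.
- **Statistical analysis plan.** SRN is analysed by a Fine and Gray model, and "all time-to-event outcomes will be compared for evidence of improvement on the pre-operative SRS/SRT arm using 1-sided tests", at a 0.10 level. No analysis of toxicity or adverse events is given.

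**The concern.** The protocol expects the experimental sequence to move two kinds of toxicity in opposite directions. A single rate that counts both can stay flat while each component changes. The two effects are also treated unequally. The anticipated benefit is isolated as SRN, has a test and contributes to the primary endpoint. The anticipated harm is not named as an outcome and has no comparison of its own. The stated purpose of comparing the yes/no rates is to find improvement, a direction in which a rise in wound complications cannot register.

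At stake is what the trial can say about the price of pre-operative treatment. Followed as written, the report could state that grade 2 or higher toxicity was similar, or showed no improvement, while wound complications were clearly more frequent in the pre-operative arm. Anyone planning a larger trial from this pilot would want that difference displayed.

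**Working it through.** **No plan figure to reproduce.** The documents state no toxicity rate, margin or test. Every rate below is an assumption chosen to show the mechanism. The only design input is 52 patients per arm (Sample size, power, and study duration). All pairs are post-operative v pre-operative.

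**Step 1: how the two sources are handled.**

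| | Delayed wound healing | Radiation necrosis |
|---|---|---|
| Direction anticipated with pre-operative treatment | More | Less |
| Own outcome | None | Time to SRN |
| Test in the SAP | None | Fine and Gray, 1-sided, α = 0.10 |
| Where it can otherwise appear | Pooled rate; CTCAE line | Pooled rate; CTCAE line; primary composite |

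The documents do not say whether SRN counts towards the pooled rate. I assume it does when it reaches grade 2.

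**Step 2: pooling.** Assume wound events of 5% v 15% and radiation toxicity of 20% v 10%.

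- No overlap between the two kinds: 5 + 20 = 25% v 15 + 10 = 25%. The difference is 0.
- Independent occurrence, pooled = 1 − (1 − wound)(1 − radiation): 1 − 0.95 × 0.80 = 24.0% v 1 − 0.85 × 0.90 = 23.5%.

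**Step 3: precision with 52 per arm.**

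- Wound events alone: SE = √(0.05 × 0.95/52 + 0.15 × 0.85/52) = 0.058, and 1.96 × 0.058 = 0.114. The difference is 10 points, 95% CI about ±11 points.
- Pooled rate, no overlap: SE = √(2 × 0.25 × 0.75/52) = 0.085, and 1.96 × 0.085 = 0.166. The difference is 0, 95% CI about ±17 points.

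**Step 4: how often an excess would be flagged.** This is an exact binomial enumeration of a z test, 1-sided at 10% in the direction of harm, with pooled rates formed under independence.

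| Assumed wound rates | Wound events alone | Pooled, other toxicity 20% v 20% | Pooled, other toxicity 20% v 10% |
|---|---|---|---|
| 2% v 10% | 73% | 30% | 5% |
| 5% v 15% | 69% | 36% | 9% |
| 10% v 20% | 57% | 34% | 10% |
| 5% v 20% | 88% | 52% | 21% |

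With the same 10-point offset placed at 15% v 5% or 30% v 20%, the last column stays within an overall range of 5% to 24%. The loss has two parts: pooling adds unrelated events (third column), and an opposing benefit then cancels much of what is left (fourth column).

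**Step 5: direction.** A 1-sided test for improvement has its rejection region on the side of lower pre-operative rates, so it cannot signal harm. In the 24.0% v 23.5% case it would declare improvement in 11% of trials, close to its nominal 10%, although the assumed wound rate has trebled.

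**The case against.** **There is another safety line.** The CTCAE item sits directly below the pooled rate, and a table of graded adverse events would normally list wound events. A reader might infer that the pooled rate is the only toxicity outcome. It is not. But the CTCAE line names no category and the SAP attaches no comparison to it, so it allows wound events to be shown without ensuring it.

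**The radiation side is visible separately.** This is true, through SRN. It lets a reader see the benefit; it does not isolate the harm.

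**The SAP does not test toxicity one-sided.** A reader might infer that it does. Its 1-sided rule covers time-to-event outcomes, and for toxicity it gives no test. The restriction to improvement comes from the wording of the objective. By-arm rates, which the objective also asks for, would show an excess in either direction. This softens the point on direction but leaves the pooling untouched.

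**The rates were chosen to cancel.** This is fair. Exact cancellation is one scenario. With no offsetting benefit, the pooled rate still flags the assumed excess in 30% to 52% of trials.

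**Separate rates would not settle the matter.** Also fair. An interval of 10 ± 11 points includes zero, and a 2-sided 5% test on 5% v 15% succeeds in only 40% of trials. The gain is in what is displayed and estimated.

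**Capture by arm.** In Arm I surgery is the last step, followed by this schedule: "After completion of radiotherapy and surgery, study subjects will be followed by Brain MRI every 2-3 months for the first year". Arm II patients return for radiation no later than 30 days after surgery. A reader might infer that early wound problems are recorded less often in Arm I. The documents do not support that. They presuppose an MRI soon after surgery, allow earlier follow-up when clinically indicated and require adverse events to go to the IRB. Nothing says the Arm II radiation visit includes a wound check.

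**Other risks of the sequence.** A reader might take delayed wound healing to be the sole harm tied to pre-operative treatment. Potential risks also discusses irradiating a lesion that turns out not to be a metastasis.

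**Conclusion.** The concern holds in limited form. A pooled rate compared for improvement is a poor instrument for the wound-healing excess that the protocol itself anticipates, and no other outcome isolates that excess. The offset could be partial or complete. In the illustration a 10-point excess disappears (about 25% v 25%), and detection of harm falls from 69% to 9%. Over all the rates tried it falls from 57–88% to 5–24% with an offsetting benefit.

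These sizes rest on assumed rates, on independence (or no overlap) between the two kinds of event, and on SRN counting towards the pooled rate. They show what can happen and do not forecast what will. The documents do not show that harm is concealed by design. The absence of a time window is, on its own, only missing detail. The primary analysis and sample size are unaffected.

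**What to change.** In Other Secondary Objectives and the Statistical analysis plan:

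1. Beside the pooled grade 2 or higher rate, report wound/surgical complications and radiation toxicity as separate rates by arm.
2. Take toxicity out of the comparison for improvements. Give each arm difference with a two-sided 95% confidence interval.
3. Count wound events over the same number of days from surgery in both arms, with the number fixed by the sponsor in advance. Counting from randomization would be unequal: surgery falls by day 15 in Arm II, but up to 15 days after the end of radiation in Arm I, which is day 30 if radiation ends on day 15.
4. Take the wound data from existing adverse-event records and post-operative notes.

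The cost is a wording change, a few more table rows and data fields, and some chart abstraction. Treatment, visits and sample size do not change. The drawback is that the separate rates will be imprecise with 52 per arm, so the report should present them as estimates and should not read an interval that includes zero as evidence of no harm.
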